2.2.2 Secondary Outcome Measures

2.2.2.1 Preliminary effectiveness: Risk of BPD

The outcome measure is change in moderate-severe BPD or death risk from baseline. Moderate-severe BPD or death risk will be defined by the NICHD Neonatal Research Network BPD outcome estimator⁴. (<https://neonatal.rti.org/index.cfm?fuseaction=BPDCalculator.start>).

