10.2 Risk of BPD

The preliminary effectiveness analysis will be on the risk of BPD which is provided by BPD estimator. The risk of BPD is presented as a % and the dichotomized the outcome will be used in the analysis (none-mild vs. moderate-severe-death). The BPD outcome estimator uses the following information to provide individual risk of BPD:

1. Gestational age (weeks)
2. Birth weight (g)
3. Sex
4. Maternal Race/Ethnicity
5. Postnatal day
6. Ventilation type (on the postnatal day of interest)
7. F_iO_2 (%) (on the postnatal day of interest)

For example, a 25 week Hispanic female with birth weight of 689 g on postnatal day 14 on mechanical ventilation with a FiO_2 of 0.45 has risk of no BPD of 1.6%, mild 27.9%, moderate 28.9%, severe 30.5%, and death 11%. Thus, none-mild risk is 29.5% and moderate-severe-death risk is 70.5%.

The risk of BPD or death as defined by the NICHD Neonatal Research Network (NRN) BPD estimator will be evaluated at baseline, on days 7, 14, 21 and 28 of study drug, the postnatal days closest to these days will be used in the BPD estimator. The postnatal day will be re-grouped to fit the BPD estimator: day 0 and day 1 will be re-grouped as day 1, day 2 and day 3 as day 3, 4-7 days as day 7, 8-14 as day 14 and 15-21 as day 21. The BPD estimator includes infants up to 28 postnatal days; for infants older than that, the 28 day estimates will be used. The birth weight used in the BPD estimator is up to 1250g, for infants with birth weight greater than 1250g, 1250g will be used. The BPD estimator includes white, black, or Hispanic infants; infants with other race/ethnicity will be excluded from the estimation. Sensitivity analyses may be done by removing infants with birth weight greater than 1250g.

The change of risk of BPD (as a percentage) from baseline to the end of study (day 28 or LOCF) will be assessed using an analysis of covariance (ANCOVA) model, with percentage change from baseline as the dependent variable. Independent factors include baseline risk percentage and dose groups.

As an exploratory analysis, a longitudinal mixed effect model may be used to test the risk of BPD at baseline and days 7, 14, 21 and 28 (with no LOCF). This longitudinal analysis will use all available risk of BPD percentages at each time point. Fixed effects will include treatment groups, dose level and dosing days; random effects will include participant. Linear and nonlinear

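### Section 10.2 analyses BPD risk as a percentage change from baseline, while 2.2.2.1 defines the outcome as a change in risk; the scale should be fixed as percentage points

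*SAP*

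**What the plan says.** Section 2.2.2.1 of the SAP sets the outcome: "The outcome measure is change in moderate-severe BPD or death risk from baseline". It names no relative scale.

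Section 10.2 says of the estimator's output that "The risk of BPD is presented as a" percentage, and works one example: "Thus, none-mild risk is 29.5% and moderate-severe-death risk is 70.5"%. It then describes the quantity to be analysed as "The change of risk of BPD (as a percentage) from baseline to the end of study" (day 28, or the last observation carried forward). The same sentence ends by specifying the ANCOVA "with percentage change from baseline as the dependent variable". On covariates it says: "Independent factors include baseline risk percentage and dose groups". It gives no formula for the dependent variable.

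For the optional longitudinal model, section 10.2 uses the risk scores themselves: "This longitudinal analysis will use all available risk of BPD percentages at each time point". In section 13, the title of Table 14.2.2 refers to change of risk and states no unit.

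**The concern.** In ordinary statistical usage a percentage change from baseline is the difference divided by the baseline value. If the ANCOVA is programmed that way, its treatment estimate does not estimate the change in risk that 2.2.2.1 defines, and it is not on the same scale as the mixed model of the same endpoint. If percentage points were meant, the clause naming the dependent variable is wrong as written. Two programmers could follow section 10.2 in good faith and report different numbers for the plan's preliminary-effectiveness analysis.

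The choice of scale matters because dividing by baseline treats equal changes in risk unequally. A given movement in points counts for more in an infant who starts low, and a rise counts for more than the fall that would undo it.

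**Working it through.** **1. The plan's own figure.** The example infant has risks of 1.6% (none), 27.9% (mild), 28.9% (moderate), 30.5% (severe) and 11% (death). None-mild is 1.6 + 27.9 = 29.5, and 100 − 29.5 = 70.5, as stated. The direct sum 28.9 + 30.5 + 11 = 70.4 differs only by rounding, since the five parts add to 99.9.

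**2. The two candidate dependent variables.** Let b be baseline risk and f end-of-study risk, both in percent.
- Point change: f − b.
- Relative change: 100 × (f − b)/b, which is the point change multiplied by 100/b.

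**3. Arithmetic of the relative scale (no assumptions).**
- A 10-point rise scores +200% from 5%, +100% from 10%, +14.2% from 70.5% and +12.5% from 80%.
- 10 to 20 scores +100%; 20 to 10 scores −50%.
- The floor is −100% at every baseline. The ceiling, 100 × (100 − b)/b, is +900% at b = 10, +400% at b = 20, +41.8% at b = 70.5 and +11.1% at b = 90.

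Because the multiplier 100/b varies between infants, residual variance depends on baseline. A linear baseline covariate adjusts the mean; it removes neither the unequal variance nor the asymmetry between rises and falls.

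**4. Size of the effect (assumed inputs).** The SAP gives no distribution of baseline risk, no SD of change and no effect size for this endpoint, so all of these are assumptions. Four groups of 30 were simulated: three furosemide doses, plus placebo pooled over cohorts (3 × 10). Baseline risk was logit-normal, the SD of the logit change was 1, and there were 1,500 runs per scenario. The model was ANCOVA on baseline and group with a 3-df F test at 0.05. The drug effect, where present, was a logit shift of −0.7 in every furosemide group. With equal weighting, the quarter of infants with the lowest baselines would carry about 0.25 of the residual sum of squares.

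| Baseline risk P10 / P50 / P90 (%) | Lowest quarter's share, no effect: relative vs points | Power with effect: relative vs points | Loss (points) |
|---|---|---|---|
| 35 / 50 / 65 | 0.41 vs 0.24 | 0.759 vs 0.771 | 1.2 |
| 22 / 50 / 78 | 0.56 vs 0.20 | 0.713 vs 0.772 | 5.9 |
| 13 / 50 / 87 | 0.65 vs 0.16 | 0.655 vs 0.723 | 6.8 |
| 56 / 70 / 82 | 0.42 vs 0.30 | 0.748 vs 0.763 | 1.5 |
| 40 / 70 / 90 | 0.59 vs 0.32 | 0.693 vs 0.747 | 5.4 |
| 26 / 70 / 94 | 0.71 vs 0.29 | 0.617 vs 0.695 | 7.8 |
| 14 / 38 / 69 | 0.54 vs 0.16 | 0.718 vs 0.735 | 1.7 |

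With the drug effect present, the lowest quarter's share was 0.37 to 0.59 on the relative scale and 0.11 to 0.26 on points. With no effect, both scales rejected about 4% to 6% of the time. Residual skewness on the relative scale reached about 1.7 with wide baselines but was near zero or negative when baselines were narrow and high.

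A separate two-group simulation (30 vs 30, 4,000 trials in each of eight logit scenarios, within-infant logit SD 0.8 to 1.0) gave power of 0.62 to 0.86 on the relative scale and 0.69 to 0.91 on points, a loss of about 4 to 10 points.

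**The case against.** The strongest reply is that no switch of endpoint was intended. Throughout section 10.2 the word percentage labels the unit of the score, and the disputed sentence itself opens by calling the quantity a change of risk expressed as a percentage. Read that way, the ANCOVA uses percentage points and agrees with 2.2.2.1. This stands as far as it goes: a reader might infer that the plan has certainly moved to relative change, and the text does not support that certainty. It does not rescue the wording, because the clause that actually names the dependent variable then says something else.

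A second reply is that the over-weighting depends on inputs the plan does not give. The only example infant sits at 70.5%, and nothing shows how many enrolled infants would start near 5% or 10%. This also stands. A reader might infer that low-risk infants always dominate the comparison. With narrow baselines the lowest quarter carried only 37% to 42% of residual variation: over-weighted, but not dominant. Nor does anything in the SAP support treating those infants' absolute risk as unimportant.

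A third tempting inference is that a few infants would reverse the apparent direction of a dose effect. It is possible in raw means: one infant going from 70 to 50 and another from 10 to 20 average −5 points, but (−28.6 + 100)/2 = +35.7% on the relative scale. Under the assumed −0.7 logit effect, however, the two scales gave opposite signs in at most about 1% of simulated trials, so this is not an expected consequence.

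The power ranking is not universal either. With a proportional effect and proportional noise, relative change had more power (for example 0.63 vs 0.56, and 0.78 vs 0.74).

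Finally, the endpoint is secondary, section 7 calls the analyses exploratory or descriptive, section 5 sizes the trial on adverse-event precision, and dose escalation in section 4.1 does not use this ANCOVA. That limits the severity. It does not excuse an estimate whose unit is either mismatched with the stated outcome or undefined.

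**Conclusion.** The point holds as an inconsistency in the scale of the endpoint. Read literally, 10.2 analyses a different quantity from the one defined in 2.2.2.1 and from the one used in its own mixed model; read generously, it contradicts itself within one sentence. That conclusion, and the lopsided bounds of the relative scale, follow from the text and arithmetic alone.

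The over-weighting of low-baseline infants appeared in every scenario run, but its degree rests on assumed baseline distributions. The cost is modest: about 1 to 10 points of power under assumed constant logit effects, with no inflation of test size. The main reason to act is that the reported estimate should measure the stated outcome. This should be corrected, but for a secondary, exploratory endpoint it is not critical.

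**What to change.** In section 10.2, replace the clause naming the dependent variable with: *the dependent variable is end-of-study risk minus baseline risk, in percentage points*. Keep baseline risk and dose group as the independent factors. Label Table 14.2.2 in percentage points so that it matches 2.2.2.1 and the mixed model. If relative change was truly intended, 2.2.2.1 and the table would instead have to say so, with the formula and the reason.

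The cost is one sentence and one table label, with no new data. The change should be made before treatment assignments are unmasked.

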3.2 Selection of Study Population

Premature infants (inpatient in neonatal intensive care units) will be randomized 3:1 to furosemide: placebo with increasing target doses of furosemide for each Cohort. There will be 40 randomized and dosed participants in each Cohort for a total of up to 120 participants.

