4 ANALYSES AND REPORTING

4.1 Dose Escalation and Halting Criteria

The trial will be halted (paused) for a safety review by the Data Monitoring Committee (DMC) if there are 4 or more Serious Adverse Reactions within a given Cohort (i.e., Cohort 1, 2, or 3). If there are <4 Serious Adverse Reactions total, the DMC will receive a summary of masked safety data and enrollment will continue in the next highest dose Cohort. Enrollment in the next highest dose Cohort will begin immediately after the 40th (or 80th) subject is enrolled and the following criteria have been met:

Table 1 Rules for advancing to next highest dose Cohort

Number of Serious Adverse Reactions	% total evaluable safety days* completed from lower dose Cohort
3	100%
2	95%
1	80%
0	70%

*% total evaluable safety days = $\frac{\text{sum of days of dosing} + 7 \text{ days of safety follow up for all participants}}{\# \text{ of participants} \times 35}$

If a 4th Serious Adverse Reaction occurs in the lower dose Cohort after enrollment begins in higher dose Cohort, enrollment will be halted for safety review but current subject dosing will continue pending DMC review. If there are 4 or more Serious Adverse Reactions, then the DMC may choose to be unmasked to treatment assignment.

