7 GENERAL ISSUES FOR STATISTICAL ANALYSIS

Descriptive statistics such as number of observations, mean, median, standard deviation, standard error, minimum and maximum will be presented by dose groups for continuous variables (such as age, weight, etc.). The dose groups will include furosemide groups (by dose level and across all dose levels), placebo group and overall. Other descriptive statistics such as counts, proportions, and/or percentages will be presented by dose groups to summarize discrete variables (such as race, sex, etc.).

Missing data will not be imputed in the non-PK analysis of this study.

Patient profile graphs showing chronologically the dosing, PK sampling, laboratory results of interest, risk of BPD, and adverse events for each participant will be developed.

All confidence intervals and tests will use $\alpha=0.05$. Analyses in this study are exploratory or descriptive in nature. No adjustments for multiplicity between endpoints are planned. Analyses will be performed using SAS Software version 9.2 or later.

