10 EFFICACY ANALYSES

10.1 Incidence of BPD

BPD will be defined by the NICHD BPD estimator as a dichotomous (none-mild vs. moderate-severe) variable and as a categorical variable (none, mild, moderate, or severe) among survivors by modifying the NIH consensus definition of BPD to include infants transferred prior to 36 weeks and the need for oxygen at 36 weeks PMA (or discharge, if sooner than 36 weeks PMA). The severity of BPD is defined as follows:

1. **No BPD:** receiving > 21% supplemental oxygen (O_2) for ≤ 28 days and not at 36 weeks PMA
2. **Mild BPD:** receiving > 21% O_2 for ≥ 28 days but not at 36 weeks PMA
3. **Moderate BPD:** receiving > 21% O_2 for ≥ 28 days plus treatment with <30% O_2 at 36 weeks PMA

4. **Severe BPD:** receiving $> 21\% \text{ O}_2$ for ≥ 28 days plus $\geq 30\% \text{ O}_2$ and/or positive pressure at 36 weeks PMA

Note that the day in the definition above is postnatal day but not treatment day. Final assessment of BPD at 36 weeks PMA will be summarized by dose groups.

BPD will be evaluated through logistic regression models by whether the event occurred or did not occur at 36 weeks PMA assessment. Independent factors in the model will include gestational age, birth weight, dose groups. Confidence intervals will be calculated using the profile-likelihood.

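### The two definite effectiveness models pool placebo over three sequential cohorts without a cohort term, so the lowest- and highest-dose contrasts are open to calendar drift

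*SAP*

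**What the plan says.** Section 3.2 of the SAP states that infants "will be randomized 3:1 to furosemide: placebo with increasing target doses of furosemide for each Cohort" and that "There will be 40 randomized and dosed participants in each Cohort for a total of up to 120 participants". The dose table in section 1.1 splits each cohort into 10 placebo and 30 furosemide infants, with one furosemide regimen per cohort. The cohorts are sequential. Under section 4.1, "Enrollment in the next highest dose Cohort will begin immediately after the 40th (or 80th) subject is enrolled", provided that the safety-day criteria are also met.

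Section 7 defines the reporting groups: "The dose groups will include furosemide groups (by dose level and across all dose levels), placebo group and overall". It describes one placebo group, which is 10 + 10 + 10 = 30 infants. The model sections use the same term without redefining it:

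- Section 10.1, logistic regression of BPD at 36 weeks PMA: "Independent factors in the model will include gestational age, birth weight, dose groups".
- Section 10.2, ANCOVA of change in BPD risk: "Independent factors include baseline risk percentage and dose groups".
- Section 10.2, optional mixed model: "Fixed effects will include treatment groups, dose level and dosing days; random effects will include participant".

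No model has a term called cohort, period or enrolment date. No analysis against concurrent placebo is named. The only sensitivity analysis in section 10.2 concerns birth weight above 1250 g.

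**The concern.** Randomisation makes a dose comparable with the 10 placebo infants of its own cohort. The other 20 infants in the pooled placebo group were enrolled in other periods and could never have received that dose. The models as written treat all 30 as equivalent controls.

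If outcomes shift over calendar time for reasons the covariates do not capture, part of the shift appears as a difference between doses. A steady improvement in care would make the lowest dose look worse than placebo and the highest dose look better, which reads as a dose-response. The BPD-risk outcome is sensitive to care practice, because apart from postnatal day its only inputs that change over time are ventilation type and FiO2. In a dose-escalation study, readers will look for exactly this pattern in the effectiveness tables.

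**Working it through.** **The SAP's own figures.** The SAP gives no power or precision for the effectiveness models. Its section 5 figures reproduce: Wilson widths of 0.222, 0.278 and 0.312 for n = 30 and 0.126, 0.164 and 0.186 for n = 90; chance of at least one 5% event 1 − 0.95^30 = 0.785 and 1 − 0.95^90 = 0.990.

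**Inputs.** Three cohorts of 10 placebo and 30 furosemide infants (sections 1.1 and 3.2); α = 0.05 (section 7), taken as two-sided. Linear drift of d residual SDs per cohort is an assumption. Residual means what is left after the model covariates.

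**Bias with no drug effect.** Set the cohort means to 0, d and 2d. Pooled placebo then has mean (0 + d + 2d)/3 = d. The contrasts against it are:

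- lowest dose: 0 − d = −d
- middle dose: d − d = 0
- highest dose: 2d − d = +d
- all furosemide: d − d = 0, because allocation is 3:1 in every cohort
- highest versus lowest dose: 2d

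**Standard errors, in SD units.**

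- dose versus pooled placebo (30 vs 30), or dose versus dose: √(1/30 + 1/30) = 0.258
- dose versus own-cohort placebo (30 vs 10): √(1/30 + 1/10) = 0.365, a ratio of 1.41
- all furosemide versus placebo (90 vs 30): √(1/90 + 1/30) = 0.211, with or without cohort in the linear model

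**False-positive rates.** Two-sided normal test, with shift d/0.258 for lowest or highest dose versus placebo and 2d/0.258 for highest versus lowest:

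| d (assumed) | Shift, dose vs placebo | Rate | Shift, highest vs lowest | Rate |
|---|---|---|---|---|
| 0 | 0 | 5% | 0 | 5% |
| 0.1 | 0.39 | 7% | 0.77 | 12% |
| 0.25 | 0.97 | 16% | 1.94 | 49% |

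A simulation of 20,000 trials per drift value, with no baseline covariate, agrees: 0.07 and 0.12 at d = 0.1; 0.12 and 0.34 at d = 0.2; about 0.20 and 0.63 at d = 0.3. With cohort indicators added, every dose contrast rejected at about 0.05 at every drift tried.

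**Binary outcome, assumed rates.** Suppose BPD falls from 50% to 40% to 30% over the cohorts with no drug effect. Pooled placebo is 40%, odds 0.667. The unadjusted odds ratios are 1.000/0.667 = 1.50 (lowest), 0.667/0.667 = 1.00 (middle) and 0.429/0.667 = 0.64 (highest).

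**The case against.** **Drift is not established.** The SAP gives no drift figure and no enrolment dates. This stands: the rates above are conditional on an assumed range.

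**Dose and time are not fully confounded.** A reader might infer that they are. The documents do not support this for dose versus placebo. Each cohort has its own placebo infants. The ANCOVA adjusts for a baseline risk built from gestational age, birth weight, sex, maternal race/ethnicity, postnatal day, ventilation type and FiO2, and the logistic model adjusts for gestational age and birth weight. Much measured case-mix drift would be absorbed. Changes in care after entry, in site mix and in unmeasured case mix would not be.

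**Highest versus lowest is not a named contrast.** Sections 10.1 and 10.2 do not specify it. The 12% to 49% applies only if someone makes that comparison.

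**Pooling is a defensible trade of bias for variance.** Root mean squared error for the lowest or highest dose versus placebo at d = 0.25 is √(0.258² + 0.25²) = 0.359 with pooled placebo and 0.365 with concurrent placebo. At d = 0.1 it is √(0.258² + 0.1²) = 0.277 against 0.365. This stands, and it is why pooled contrasts should be kept. It does not excuse leaving out the concurrent comparison or the caveat.

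**Cohort is added where there is no bias.** The all-furosemide contrast is already unbiased at exact 3:1. Adding cohort still removes drift from the residual: in simulation at d = 0.5 the unadjusted test rejected at 0.034 and the adjusted test at 0.049. It also protects the contrast if exclusions disturb the ratio.

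**The analyses are not confirmatory.** Section 7 says "Analyses in this study are exploratory or descriptive in nature", safety is the primary objective, and effectiveness is labelled preliminary. This lowers the severity but does not make a drift-prone contrast informative.

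**Conclusion.** The point holds for the dose-level contrasts in the logistic model and the ANCOVA. In both, 20 of the 30 controls for any dose were not randomised against it, and no term or sensitivity analysis makes use of the within-cohort randomisation.

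Under an assumed linear residual drift of 0.1 to 0.25 SD per cohort, the lowest- and highest-dose contrasts carry a bias of that size in opposite directions, with the false-positive rates tabulated above. The middle-dose contrast is unbiased only if drift is linear. The all-furosemide contrast relies on 3:1 allocation holding among the infants analysed.

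A reader might go further and conclude that the plan will report drift as a dose effect, or that pooling placebo is an error. The documents show neither: drift may be absent or captured by covariates, and pooling is the more precise choice when drift is small. The optional mixed model is a separate case. It would carry cohort if placebo infants take their cohort's dose level, but the SAP does not say what level they take. Severity is moderate to low.

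**What to change.** Amend sections 10.1 and 10.2 before unmasking:

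1. Include cohort as a factor in the all-furosemide-versus-placebo contrast. In the linear model with 3:1 allocation in every cohort this costs essentially no precision (SE 0.211 SD). A small loss is possible in the logistic model, or where exclusions are uneven: section 10.1 classifies BPD among survivors, and section 10.2 leaves infants of other race/ethnicity out of the estimator.
2. Keep the dose versus pooled-placebo contrasts. Pre-specify, as a sensitivity analysis, each dose against its own cohort's placebo infants (cohort plus treatment within cohort).
3. State that dose contrasts using pooled placebo are only partly randomised comparisons, and that dose-versus-dose differences are not randomised.
4. In the optional mixed model, set the dose level of placebo infants to their cohort's level, so that the model carries cohort.

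The cost is SAP wording and one extra model per endpoint, with no change to design, data collection or sample size. The downside is that the concurrent contrasts have a 41% larger SE (0.365 against 0.258 SD). They have limited power, and their agreement with the pooled results would be only weak reassurance.

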trends of the drug effect for both overall and individual level data will be evaluated. An unstructured covariance matrix will be used initially to model the co-variance of repeated measures within participants, but other co-variance structures will be explored and the best structure will be chosen based on Akaike's Information Criteria.

Potential biomarkers (i.e. IL-1, IL-6, IL-8, TNF- α , and RANTES) may be included in the models mentioned above.

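### If fitted as listed, the optional longitudinal model of BPD risk averages a pre-dose visit into the drug effect, and its planned trend evaluation has no matching model term

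*SAP*

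**What the plan says.** SAP section 10.2 states that "a longitudinal mixed effect model may be used to test the risk of BPD at baseline and days 7, 14, 21 and 28", using observed values without LOCF. Baseline is therefore a response, not a covariate. The model terms are: "Fixed effects will include treatment groups, dose level and dosing days; random effects will include participant". No product of treatment or dose with day appears.

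The next sentence says that linear and nonlinear "trends of the drug effect for both overall and individual level data will be evaluated". It names no model term, contrast or time axis. On covariance: "An unstructured covariance matrix will be used initially to model the co-variance of repeated measures within participants", after which other structures are tried and one is chosen by AIC.

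Two other places bear on the reading. For the main effectiveness analysis, an ANCOVA of change to day 28 or LOCF, section 10.2 says "Independent factors include baseline risk percentage and dose groups", so baseline is handled there as a covariate. Section 7 says "The dose groups will include furosemide groups (by dose level and across all dose levels), placebo group and overall", which makes dose level a grouping of participants. It is not a quantity that is zero before dosing and positive afterwards.

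The longitudinal model is labelled exploratory, and section 7 calls all analyses exploratory or descriptive. Section 13 nevertheless reserves an efficacy table for it (14.2.3).

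**The concern.** Under randomisation the expected group difference before the first dose is zero. A model with a between-participant treatment term and no interaction with day forces one common group difference on every visit. If baseline is one of those visits, its zero is averaged in, and the coefficient is not the effect at day 28 or at any other visit.

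The trend sentence pulls the other way. A trend of the drug effect over dosing days is a treatment-by-day interaction, which the list lacks. The drug-effect parameter to be tested is thus left open between a diluted average and an unnamed interaction.

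What is at stake is the reading of table 14.2.3. This is the only analysis of the risk score that uses all visits and avoids LOCF, so readers may set it beside the ANCOVA to judge whether LOCF mattered. A smaller coefficient caused by the model's form could be mistaken for a missing-data effect.

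**Working it through.** **Inputs from the SAP.** Five response times: baseline and days 7, 14, 21 and 28 (10.2). Fixed effects as listed (10.2). Participants "will be randomized 3:1 to furosemide: placebo with increasing target doses of furosemide for each Cohort" (3.2), in three cohorts of 30 furosemide and 10 placebo (1.1), so 90 against 30 in total. Alpha is 0.05 (section 7), taken as two-sided.

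**Inputs assumed.** The SAP gives no SD, within-participant correlation or effect size for the risk score. Assumed: equal variances; compound symmetry (CS) or AR(1) with correlation ρ from 0.3 to 0.9; complete data; for power, a day-28 effect of 0.5 SD.

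**The plan's own figures.** There are none for this model. Section 5 covers safety precision only, and its detection chances reproduce: 1 − 0.95^30 = 0.785 and 1 − 0.95^90 = 0.990, against the stated 79% and 99%.

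**Step 1: weights.** With day as a factor and covariance matrix S over the five visits, the expected treatment coefficient is Σ w_j e_j. Here e_j is the true effect at visit j (zero at baseline) and w = S⁻¹1 / (1′S⁻¹1).
- CS: every weight is 1/5.
- AR(1): baseline and day 28 each get 1/(5 − 3ρ); each middle visit gets (1 − ρ)/(5 − 3ρ).

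**Step 2: constant post-baseline effect.** Share recovered = 1 − baseline weight.

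| Structure | Baseline weight | Share recovered |
|---|---|---|
| CS, any ρ | 0.20 | 0.80 |
| AR(1), ρ = 0.3 | 1/4.1 = 0.244 | 0.756 |
| AR(1), ρ = 0.5 | 1/3.5 = 0.286 | 0.714 |
| AR(1), ρ = 0.7 | 1/2.9 = 0.345 | 0.655 |
| AR(1), ρ = 0.9 | 1/2.3 = 0.435 | 0.565 |

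**Step 3: effect growing linearly to day 28.** e = (0, 0.25, 0.5, 0.75, 1). The weights are symmetric about day 14, so the share is 0.50 of the day-28 effect in both structures. For CS: 0.2 × 2.5 = 0.50. For AR(1) with ρ = 0.7: 0.345 × 1 + 0.103 × 1.5 = 0.50.

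**Step 4: would removing baseline be enough?** With days 7–28 only, a constant effect is recovered in full (1.00). A linear effect reaches only (0.25 + 0.5 + 0.75 + 1)/4 = 0.625 of its day-28 value. The interaction is needed as well.

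**Step 5: unequal variances.** The range above is not a bound. With AR(1) ρ = 0.8 and a baseline SD 0.7 times the day-28 SD, the shares are 0.31 (constant) and 0.23 (linear). With a baseline SD 1.3 times the day-28 SD they are 0.79 and 0.70. Nothing in the SAP shows which case applies.

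**Step 6: power** (normal approximation, 0.5 SD at day 28). With 90 against 30, f = √(1/90 + 1/30) = 0.211. SE of the main effect = f/√(1′S⁻¹1). SE of the day-28 contrast with equal baseline means = f√(1 − r²), where r is the correlation of baseline with day 28.

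| Scenario | Listed main effect | Day-28 contrast |
|---|---|---|
| 90 vs 30, linear, CS 0.7 | 27% | 91% |
| 90 vs 30, linear, AR(1) 0.7 | 34% | 69% |
| 90 vs 30, constant, AR(1) 0.5 | 73% | 66% |
| 30 vs 30, constant, CS 0.3 | 65% | 53% |
| 30 vs 30, constant, AR(1) 0.3 | 74% | 49% |

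First row: 0.25/0.184 − 1.96 = −0.60, giving 27%; 0.5/0.151 − 1.96 = 1.36, giving 91%. The ordering reverses for a constant effect at low correlation.

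**The case against.** The strongest reply is that the list is not declared complete and that the next sentence commits to trends of the drug effect at overall and individual level. In a longitudinal model the natural reading is a trend over dosing days. That needs a treatment-by-day term, and an effect read from a suitable interaction is not diluted. This stands, so a reader who infers that the planned result is certain to be biased goes further than the SAP supports. It does not remove the point: the term, the contrast and the time axis are all unstated, and the sentence could also mean a trend over dose.

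A reader might also infer a certain loss of power. The calculations contradict that: for a constant effect and low correlation the averaged test is the stronger one. Under the null hypothesis it also remains a valid test.

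Nor should any gap between this model and the ANCOVA be put down to this fault alone. The two differ by design in the response, the visits used and LOCF.

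Two side issues are weaker still. Treatment group is aliased with dose level if dose level is a four-level factor including placebo. It is not if dose level means cohort, since each cohort has its own placebo infants; the SAP does not fix the coding. A random participant intercept beside an unstructured covariance is redundant and not separately identifiable, but it does not bias the fixed effects, and the AIC step may replace that structure.

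**Conclusion.** The point holds conditionally. If the model is fitted with the listed terms only, its treatment coefficient understates the drug effect. Under equal variances and assumed correlations of 0.3 to 0.9, it gives about 57–80% of a constant post-baseline effect and 50% of the day-28 effect when the effect grows linearly. If an interaction is added to serve the trend sentence, the dilution can be avoided, but the SAP does not name that term. The firm finding is that the list of fixed effects and the trend sentence do not fit together and that the tested parameter is unspecified.

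The documents do not support a claim of certain dilution, certain loss of power or any fault in the ANCOVA. Severity is low, because the model is exploratory and optional and safety is the primary outcome.

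**What to change.** In section 10.2, replace the listed terms with one four-level dose-group factor (placebo and three furosemide levels), dosing day as a factor, and dose group-by-day. Then:

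- Either keep baseline as a response and constrain the group means to be equal there, or use baseline risk as a covariate with days 7–28 as responses.
- Name the day-28 contrast of each furosemide level against placebo as the reported effect. Trend contrasts over days can be reported beside it, with a statement of whether trend over dose is also meant.
- Omit the random participant intercept when the unstructured covariance is used. Keep it only with a simpler residual structure.

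Day should be a factor for the day-28 contrast. With a straight-line day-by-treatment term under CS (ρ = 0.7), a constant effect of 1 would be fitted as 0.4 + 28 × 0.0286 = 1.2 at day 28.

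The cost is SAP wording and a few parameters: with equal baseline means, four days by three dose contrasts gives 12 group parameters in place of three. No new data are needed.
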